6.1.5. Analysis Visit Windows

Visits will be analyzed as scheduled. The windows follow the Schedule of Events in the Protocol. Screening, enrollment, and Day 1 of the Treatment Period can take place on the same day if the required screening test results are available.

6.1.6. Pooling of Sites

There will be no pooling of sites for this study.

6.1.7. Derived Variables

- Respiratory failure is defined as the requirement for use of intubation/mechanical ventilation, an oxygen rate with high flow nasal cannula greater than 20 L/min, non-invasive positive pressure respiratory support, or ECMO, or clinical diagnosis of respiratory failure.
- Respiratory failure-free survival is defined as the combination of no respiratory failure (defined above) and no report of mortality from any cause.
- Mortality from any cause is defined as death listed on the Study Completion CRF or WHO 9-point ordinal scale assessment of death.
- Non-invasive positive pressure respiratory support is defined as the use of continuous positive airway pressure (CPAP) or bilevel positive airway pressure (BiPAP).
- Ventilator use is defined as the use of mechanical ventilation, CPAP, or BiPAP.
- Organ failure is defined as a reported AE indicating a ‘failure’ of respiratory, cardiovascular, hepatic, renal, coagulation, or neurological reported at the PT level or

‘insufficiency’ reported as the lowest level term.

- Renal stabilization or replacement is defined as reported use of any type of dialysis in concomitant medications with a route recorded as (“HEMODIALYSIS”, “PERITONEAL DIALYSIS”, or “DIALYSIS”).
- Time to initiation of supplemental oxygen or other respiratory support in the first 28 days after randomization = (the earliest of Day 28 or date/time of the first use – date/time of randomization) + 1.
- Duration of supplemental oxygen or other respiratory support in the first 28 days after randomization = (the earliest of Day 28 of the study or date/time of the last use – the latest of date/time of the first supplemental oxygen or other respiratory support or date/time of randomization) + 1.
- Time to initiation of intubation/mechanical ventilation, an oxygen rate with high flow nasal cannula greater than 20 L/min, non-invasive positive pressure respiratory support, ECMO in the first 28 days after randomization = (the earliest of Day 28 or date/time of the first support – date/time of randomization) + 1.
- Duration of intubation/mechanical ventilation, an oxygen rate with high flow nasal cannula greater than 20 L/min, non-invasive positive pressure respiratory support, or ECMO in the first 28 days after randomization = (the earliest of Day 28 of the study or date/time of the last specified respiratory support – the latest of date/time of the first specified respiratory support or randomization) + 1.
- For the time till all-cause mortality Cox proportional hazards model, time to all-cause mortality or censoring will be calculated as follows
 - If mortality occurs within 60 days post-randomization; then Time to all-cause mortality or censoring = date/time of death – date/time baseline + 1.
 - If mortality occurs on or after 60 days post-randomization; then Time to all-cause mortality or censoring = 60 days.
 - If mortality does not occur, and last follow-up is prior to 60 days; then Time to all-cause mortality or censoring = date/time of last follow-up – date/time baseline + 1.
 - If mortality does not occur, and last follow-up is on or after 60 days; then Time to all-cause mortality or censoring = 60 days.
- Change from baseline = value at current time point – value at baseline.
- TEAE = any adverse event with an onset or worsening date/time after the date/time of the first administration of IP and prior to the 30 days after last dose of IP.

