CRITERIA FOR EVALUATION	
Efficacy endpoints:
 
Primary efficacy endpoint:
 
 
• Proportion of participants alive and free of respiratory failure at Day 28 (respiratory failure is defined in exclusion criterion 1.c.i)
 
 
Secondary efficacy endpoints:
 
 
• Clinical improvement as measured by the World Health Organization (WHO) 9-point ordinal scale from baseline through Day 60
 
• Time to and proportion of subjects with all-cause mortality through Day 60
 
• Proportion of participants who experienced respiratory failure within the first 28 days after randomization
 
• Among patients that never experience respiratory failure in the first 28 days, time to initiation, duration, and proportion of subjects receiving supplemental oxygen or other respiratory support within the first 28 days after randomization
 
• Among patients that experience respiratory failure in the first 28 days, time to initiation and duration of the forms of respiratory support meeting criteria outlined in critical COVID criteria (exclusion criteria 1.c.i) within the first 28 days after randomization
 

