## 7. STUDY DESIGN

### 7.1. Overall Study Design and Plan

This is a 2-part, multi-center, randomized, double-blind, placebo-controlled, phase 2 study designed to evaluate the safety, tolerability, and efficacy of oral varespladib, in addition to standard of care, in patients hospitalized with severe COVID-19 caused by SARS-CoV-2.

Approximately 90 participants will be randomized, 18 in Part 1 and 72 in Part 2. Participants must be 18 to 80 years of age and have severe laboratory-confirmed COVID-19.

The study will be conducted in 2 parts. Both parts will be randomized and double-blind. Part 1 will be dose-finding in 4 parallel treatment groups randomized to treatment with varespladib (at 250 mg once daily [QD], twice daily [BID], or three times daily [TID] [total doses of 250, 500, or 750 mg/day]) or placebo in a 5:5:5:3 ratio. After all participants in Part 1 have completed Day 28, a data safety monitoring board (DSMB) will review results from Part 1 and will recommend the dose regimen to be used in Part 2. Part 2 will randomize an additional 72 participants to the dose regimen selected from Part 1 or placebo in a 1:1 ratio.

In both parts of the study, eligible participants will be enrolled and randomized to receive either varespladib or placebo in addition to institutional standard of care for 7 days (7 complete days of study drug administration after randomization).

Participants will be assessed daily per standard of care while hospitalized and on a regular basis after discharge. The Day 1, 4, 7, 14, and 28 visits will be performed in person (either at the hospital/site or via a home health provider) to assess safety, obtain blood and urine samples for laboratory tests, and obtain clinical outcome data. The Day 2, 3, 5, 6, 8, 9, 10, 11, 12, 13, 15, 16, 17, 18, 19, 20, 21, 45, and 60 visits for discharged participants may be conducted by phone or via electronic patient-reported outcome (ePRO) devices.

Efficacy will be assessed by respiratory failure-free survival at Day 28. For the purposes of this protocol, respiratory failure is defined as a subject requiring:

- Endotracheal intubation and mechanical ventilation
- Oxygen delivered by high-flow nasal cannula ([HFNC] heated, humidified, oxygen delivered via reinforced nasal cannula at flow rates > 20 L/min with fraction of delivered oxygen  $\geq 0.5$ )
- Noninvasive positive pressure ventilation
- extracorporeal membrane oxygenation (ECMO), or

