2.2.1.2. Secondary Efficacy Endpoint(s)

The secondary efficacy endpoints of this study include the following:

- Clinical improvement as measured by the World Health Organization (WHO) 9-point ordinal scale from baseline through Day 60
- Time to and proportion of participants with all-cause mortality through Day 60
- Proportion of participants who experienced respiratory failure within the first 28 days after randomization
- Among patients that never experience respiratory failure in the first 28 days, time to initiation, duration, and proportion of subjects receiving supplemental oxygen or other respiratory support within the first 28 days after randomization
- Among patients that experience respiratory failure in the first 28 days, time to initiation and duration of the forms of respiratory support meeting criteria outlined in critical COVID criteria (exclusion criteria 1.c.i) within the first 28 days after randomization
- Number of days of oxygen support through Day 28 after randomization
- SpO₂ through Day 28 after randomization

- Number of ventilator-free days through Day 28 after randomization
- Number of hospitalization days through Day 28 after randomization
- Number of days without renal stabilization and/or replacement through Day 28 after randomization
- Number of organ failure-free days through Day 28 after randomization
- Number of days at elevated level of care (ICU) through Day 28 after randomization
- Number of healthcare encounters through Day 28 after randomization

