8.1. Primary Efficacy Analysis

The primary efficacy endpoint is the proportion of participants alive and free of respiratory failure at Day 28.

The proportion of respiratory failure-free surviving participants in each Part 2 treatment group at Day 28 will be analyzed using logistic regression with treatment as a factor and age, diabetes, body mass index, and baseline sPLA2 activity included as covariates. Dummy/reference coding will be used in all logistic regression implementations. The risk difference between varespladib and placebo along with the 95% CI and p-value will be presented. Note that logistic regression typically involves calculation and testing of odds ratios, however, this analysis will focus on presenting and testing the risk difference via the delta method ([Ge et al, 2011](#)).

The ITT, PP and Combined populations will be used to analyze the primary efficacy endpoint. The ITT population will be the primary population for the efficacy analyses.

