8.2.2. All-Cause Mortality

All-cause mortality from randomization through Day 60 will be analyzed using a Cox-Proportional hazard model. The number of participants who experience the event and rate ratio with 95% CI will be presented. The p-value to test if the rate ratio between treatments differs from 1 will be evaluated. Kaplan-Meier methodology will be used to estimate the median time to the event and 95% CI. Time to all-cause mortality will be calculated according to [Section 6.1.7](#).

Censoring events include loss to follow-up prior to Day 60. Covariates will include those a priori specified in [Section 6.1.2](#), and Efron's method for handling tied time-to-events will be used. The p-value testing for non-zero treatment effect will be obtained from a Wald chi-square test, and

the 95% CI associated with the treatment effect will be a Wald-type CI.

Additionally, the proportion of participants who die will be analyzed using the same logistic regression and risk difference method with dummy coding as the primary endpoint (Ge et al, 2011). In general, the proportions of participants with an event on or before Day 60 will be analyzed.

8.2.3 Proportion of participants who experienced respiratory failure within the first 28 days after randomization

The proportion of participants experiencing respiratory failure from randomization through Day 28 will be analyzed using the same logistic regression and risk difference method with dummy coding as the primary endpoint. Respiratory failure is defined as defined by requiring HFNC >20 L/min, non-invasive positive pressure ventilation, mechanical ventilation, or ECMO, or clinical diagnosis of respiratory failure (exclusion criteria 1.c.i) at any time during the 28 days after randomization. Note that those who experience mortality after respiratory failure are still counted towards this analysis. Those who experience mortality without prior respiratory failure will not be counted towards this analysis.

8.2.4 Among patients that do not experience respiratory failure in the first 28 days, time to initiation and duration of supplemental oxygen or other respiratory support within the first 28 days

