The number of days of supplemental oxygen or other respiratory support in patients not meeting the criteria for respiratory failure from randomization through Day 28 will be summarized descriptively and analyzed using ANCOVA. The LS means will be presented along with the associated 95% CI within each treatment group. In comparing treatments, LS mean differences between treatments will be presented along with associated 95% CIs and p-values. For Part 1 analysis, this endpoint will be reported in all patients in the ITT population.

The time to start of supplemental oxygen or other respiratory support from randomization through Day 28 will be analyzed using a Cox-Proportional hazard model. The number of participants who experience the event and rate ratio with 95% CI will be presented. The p-value to test if the rate ratio between treatments differs from 1 will be evaluated. Kaplan-Meier methodology will be used to estimate the median time to the event and 95% CI. Censoring events include loss to follow-up prior to Day 28. Mortality will not be considered a censoring event and instead will be analyzed as if this patient was on supplemental oxygen or other respiratory support for all days between randomization and Day 28. If mortality or the event of interest does not occur, all subjects will be censored at Day 28. Covariates will include those a priori specified in [Section 6.1.2](#), and Efron's method for handling tied time-to-events will be used. The p-value testing for non-zero treatment effect will be obtained from a Wald chi-square test, and the 95% CI associated with the treatment effect will be a Wald-type CI.

Duration and time to supplemental oxygen or other respiratory support through Day 28 will be calculated according to [Section 6.1.7](#)

8.2.5. Among patients that experience respiratory failure in the first 28 days, time to initiation and duration of the forms of respiratory support meeting criteria outlined in critical COVID criteria (exclusion criteria 1.c.i) within the first 28 days

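### SAP 6.1.7 drops the protocol's oxygen-fraction condition from the high-flow item of respiratory failure, so the primary endpoint rests on a broader event than the protocol's, and SAP section 10 does not say so

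*SAP*

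**What the plan says.** **Protocol.** The primary endpoint is given in the Synopsis as "Proportion of participants alive and free of respiratory failure at Day 28 (respiratory failure is defined in exclusion criterion 1.c.i", and section 13.1.4.1 repeats the reference to that criterion. Criterion 1.c.i (Synopsis and section 8.2.2), restated in section 7.1, describes the HFNC item as oxygen through a "reinforced nasal cannula at flow rates > 20 L/min with fraction of delivered oxygen" of at least 0.5. Both conditions must be met. The clinical-diagnosis item is limited to cases where one of the listed therapies is needed but cannot be given because resources are short.

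**SAP, primary endpoint.** Section 6.1.7 says: "Respiratory failure is defined as the requirement for use of intubation/mechanical ventilation, an oxygen rate with high flow nasal cannula greater than 20 L/min". It then lists non-invasive positive pressure support, ECMO and clinical diagnosis. No oxygen fraction appears, and the clinical-diagnosis item has no resource-limitation qualifier. The composite follows directly: "Respiratory failure-free survival is defined as the combination of no respiratory failure (defined above) and no report of mortality from any cause". Section 8.1 analyzes it: "The proportion of respiratory failure-free surviving participants in each Part 2 treatment group at Day 28 will be analyzed using logistic regression". Neither 8.1 nor the endpoint statement in 2.2.1.1 cites 1.c.i.

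**SAP, secondary endpoints.** Section 8.2.3 counts participants "requiring HFNC >20 L/min, non-invasive positive pressure ventilation, mechanical ventilation, or ECMO, or clinical diagnosis of respiratory failure (exclusion criteria 1.c.i"; it cites the criterion but spells out flow alone. Section 2.2.1.2 refers to "forms of respiratory support meeting criteria outlined in critical COVID criteria (exclusion criteria 1.c.i) within the first 28 days after randomization", and the heading of 8.2.5 does likewise. Section 8.2.5 nevertheless sends its calculation to 6.1.7, where the time and duration bullets for this support again use flow alone.

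**SAP section 10** covers the recruitment pause, the Part 1 reporting changes and the removal of subsetting for 8.2.4 and 8.2.5. It does not mention the failure definition.

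**The concern.** One endpoint label carries two rules. The protocol defines the endpoint and the SAP holds the derivation, so a reader of the results would assume the protocol definition while the programmed variable follows 6.1.7. If any participant received HFNC above 20 L/min at a fraction below 0.5, the two documents would classify that participant differently.

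Eligibility adds to this. Criterion 1.c.i is also an exclusion rule, and its HFNC item does not exclude a patient above 20 L/min at a fraction below 0.5. Under the SAP such a patient, if enrolled, could be a failure from Day 1, before treatment could act. Protocol section 7.2 speaks of leaving out patients who already need oxygen support, but the criteria in 8.2.2 contain no such general item.

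The Part 2 amendment announced in SAP section 10 is described as serving the secondary endpoints in 8.2.4 and 8.2.5. As written, it does not take in the primary definition.

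**Working it through.** The documents give no power calculation or event rate, so there is no planned figure to reproduce. The check is a comparison of the two rules, followed by the weight of one participant.

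**1. The HFNC item, all other items held equal and absent**

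| Flow > 20 L/min | Fraction ≥ 0.5 | Protocol 1.c.i | SAP 6.1.7 |
|---|---|---|---|
| no | no | not failure | not failure |
| no | yes | not failure | not failure |
| yes | yes | failure | failure |
| yes | no | **not failure** | **failure** |

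If another failure criterion is met, both rules give failure. There is one discordant pattern and it goes one way: on this item the SAP event contains the protocol event. The missing resource-limitation qualifier can also only add failures.

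**2. Weight of one reclassified participant**

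Arm sizes come from the allocations in protocol 13.2 and SAP 3.2: 5:5:5:3 in Part 1 (18), and 72 at 1:1 in Part 2 (72/2 = 36 per arm). The change in the failure-free proportion is 1/n.

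- Part 1 varespladib arm: 1/5 = 20.0 points.
- Part 1 placebo arm: 1/3 = 33.3 points.
- Planned Part 2 arm: 1/36 = 2.8 points.

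Section 10 promises confidence intervals for Part 1. With exact 95% intervals (my choice of method), 5/5 (47.8% to 100%) becomes 4/5 (28.4% to 99.5%), and 3/3 (29.2% to 100%) becomes 2/3 (9.4% to 99.2%).

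**3. Part 2 risk difference, illustration only**

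Let p1 and p0 be the failure-free proportions under the protocol rule, and r1 and r0 the shares of those successes that the SAP rule reclassifies, on varespladib and placebo. The SAP-rule difference is p1(1 − r1) − p0(1 − r0). The documents give none of these values. I assume p1 = 0.85 and p0 = 0.70 (15 points), without covariate adjustment.

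| r1 | r0 | Calculation | Difference |
|---|---|---|---|
| 5% | 5% | 0.8075 − 0.6650 | 14.25 points |
| 10% | 10% | 0.765 − 0.630 | 13.5 points |
| 20% | 20% | 0.68 − 0.56 | 12 points |
| 10% | 5% | 0.765 − 0.665 | 10 points |
| 5% | 10% | 0.8075 − 0.6300 | 17.75 points |

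Equal rates shrink the difference in proportion. Unequal rates can move it either way.

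**The case against.** The best defence is that the SAP text is shorthand. SAP section 1 names the protocol as reference material. Section 8.2.3 prints the short list and labels it 1.c.i, which suggests the author regarded the two as the same. The protocol places flow and oxygen fraction together in the parenthesis that describes HFNC, so the SAP's mention of HFNC could be read as that term. This is plausible, and no intent to change the endpoint is shown. It does not settle the matter. The SAP restates the flow limit and leaves the fraction out in four places (three bullets of 6.1.7 and the text of 8.2.3), the citations of 1.c.i sit only in secondary-endpoint text, and 6.1.7 is the only definition the SAP offers for the primary endpoint.

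Other objections stand in part:

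- The comparison covers the HFNC item. SAP 6.1.7 also words non-invasive support as CPAP or BiPAP; that does not clearly narrow the event, but the net effect of every wording difference was not tested.
- In 8.2.3 the citation of 1.c.i directly follows the clinical-diagnosis item and may bring the resource-limitation qualifier in by reference. In 6.1.7 there is no such citation.
- Part 2 had one participant at the pause, so step 3 shows how the rule behaves and is not a forecast. In arms of 5 and 3, any single event moves the result by 20 or 33.3 points.
- The text of the planned amendment is not available, and it might be drafted more widely than section 10 describes.
- The schedule of events names no oxygen-fraction item, but it names no flow item either, so its silence does not show that the fraction went unrecorded.

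**Conclusion.** The concern holds. Followed as written, SAP 6.1.7 would count as failures some participants whom the protocol's primary endpoint counts as successes, and section 10 does not disclose this. The direction is certain on the HFNC item: the failure-free proportion is equal or lower under the SAP. The size is unknown and may be zero, because the documents do not show that anyone had the discordant pattern. Per participant it is 20, 33.3 or 2.8 points in arms of 5, 3 and 36. The Part 2 risk differences in the working rest wholly on assumed proportions and rates.

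The secondary endpoints are internally inconsistent rather than plainly redefined. The stakes are limited: SAP 4.1 calls the study exploratory, and Part 1 (N = 18) is reported descriptively, with confidence intervals and no efficacy p-values. It should still be fixed, because it concerns the primary endpoint and the correction is small. This is a point about consistency between documents; it does not say which definition is clinically right.

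**What to change.** 1. In the three flow-only bullets of SAP 6.1.7 (respiratory failure; time to, and duration of, the critical forms of support) and in the text of 8.2.3, state flow above 20 L/min and delivered oxygen fraction of at least 0.5 as joint conditions, as in protocol 1.c.i.
2. In the first bullet of 6.1.7 and in 8.2.3, restore the resource-limitation qualifier on clinical diagnosis.
3. Do this before the Part 1 database lock if that has not occurred, and widen the planned Part 2 amendment to cover the primary definition.
4. Where the oxygen fraction was not recorded, or if flow alone is intended, list and justify the difference in SAP section 10 and report the flow-only result under its own label.

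The cost is SAP wording, a programming change, and a check of the eCRF and source records. That check matters: protocol 10.3.1.1 leaves the assessment of oxygen support to institutional practice, and the data collection documents that the SAP mentions are not among those reviewed. If the fraction was not captured in Part 1, only step 4 can be applied there to the HFNC item.

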- Clinical diagnosis of respiratory failure (i.e., clinical need for one of the preceding therapies, but preceding therapies not able to be administered in setting of resource limitation)

Safety will be assessed by evaluating AEs, vital sign measurements, use of oxygen therapies, changes in levels of biomarkers, clinical laboratory test results, ECGs, physical examination findings, and concomitant medications and therapies. A DSMB will evaluate safety data at specified intervals during both parts of the trial.

All AEs observed by the study personnel or reported by the participant during the study (from the time of the signing of the informed consent through Day 60) will be documented.

PK samples will be drawn from all participants in Part 1 and in a subset of approximately 14 participants in Part 2 in order to enable estimation of PK parameters in approximately 22 participants receiving active treatment with varespladib.

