#### 8.2.2 Exclusion Criteria

A participant will be excluded from the study if he or she meets any of the following criteria:

1. Participant has mild, moderate, or critical COVID-19 defined in accordance with the FDA Guidance for Industry:

- a. Mild COVID-19:
  - i. Symptoms of mild illness with COVID-19 that could include fever, cough, sore throat, malaise, headache, muscle pain, gastrointestinal symptoms, without shortness of breath or dyspnea
  - ii. No clinical signs indicative of moderate, severe, or critical severity
- b. Moderate COVID-19:
  - i. Symptoms of moderate illness with COVID-19, which could include any symptom of mild illness (fever, cough, sore throat, malaise, headache, muscle pain, gastrointestinal symptoms) or shortness of breath with exertion
  - ii. Clinical signs suggestive of moderate illness with COVID-19, such as respiratory rate  $\geq 20$  breaths per minute, peripheral oxygen saturation ( $\text{SpO}_2$ )  $> 93\%$  on room air at sea level, heart rate  $\geq 90$  beats per minute
  - iii. No clinical signs indicative of severe or critical illness
- c. Critical COVID-19:
  - i. Respiratory failure defined based on resource utilization requiring at least one of the following:
    - Endotracheal intubation and mechanical ventilation
    - Oxygen delivered by high-flow nasal cannula ([HFNC] heated, humidified, oxygen delivered via reinforced nasal cannula at flow rates  $> 20$  L/min with fraction of delivered oxygen  $\geq 0.5$ )
    - Noninvasive positive pressure ventilation
    - ECMO, or
    - Clinical diagnosis of respiratory failure (i.e., clinical need for one of the preceding therapies, but preceding therapies not able to be administered in setting of resource limitation)
  - ii. Shock (defined by systolic blood pressure  $< 90$  mmHg, or diastolic blood pressure  $< 60$  mmHg or requiring vasopressors)
  - iii. Multi-organ dysfunction/failure

2. Participant has taken investigational medications within 7 days or 5 half-lives prior to enrollment, whichever is shorter.
3. Participant has required any new form of sedation, anxiolysis or central nervous system (CNS) depressant within the 48 hours prior to enrollment that would interfere with neurologic assessments at enrollment.
4. Has history of cerebrovascular accident or intracranial bleeding of any kind, acute coronary syndrome, myocardial infarction, or severe pulmonary hypertension.

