#### **13.1.4.1 Efficacy Endpoints**

The primary endpoint is the proportion of participants alive and free of respiratory failure at Day 28 (respiratory failure is defined in exclusion criterion 1.c.i).

The secondary efficacy endpoints are:

- Clinical improvement, as measured by the World Health Organization (WHO) 9-point ordinal scale through Day 60
- Time to and proportion of subjects with all-cause mortality through Day 60
- Proportion of participants who experienced respiratory failure in the first 28 days
- Among patients that never experience respiratory failure in the first 28 days, time to initiation, duration, and proportion of subjects receiving supplemental oxygen or other respiratory support within the first 28 days after randomization
- Among patients that experience respiratory failure in the first 28 days, time to initiation and duration of the forms of respiratory support meeting criteria outlined in critical COVID criteria (exclusion criteria 1.c.i) within the first 28 days after randomization
- Number of days of oxygen support through Day 28 after randomization
- SpO2 through Day 28 after randomization
- Number of ventilator-free days through Day 28 after randomization
- Number of hospitalization days through Day 28 after randomization
- Number of days without renal stabilization and/or replacement through Day 28 after randomization
- Number of organ failure-free days through Day 28 after randomization
- Number of days at elevated level of care (ICU) through Day 28 after randomization
- Number of healthcare encounters through Day 28 after randomization

The exploratory efficacy endpoints are:

- sPLA2 within blood samples from treatment initiation to Day 28 after randomization

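### SAP 6.1.7 counts a clinical diagnosis of respiratory failure towards the primary endpoint without the protocol's condition that a listed therapy was needed but unavailable

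*SAP*

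**What the plan says.** **Protocol.** Section 13.1.4.1 fixes the meaning of the primary endpoint: "respiratory failure is defined in exclusion criterion 1.c.i". The synopsis and Section 6 make the same link. Criterion 1.c.i (Section 8.2.2) lists intubation with mechanical ventilation, high-flow nasal oxygen, noninvasive positive pressure ventilation and ECMO. It then adds a clinical-diagnosis limb, explained as "clinical need for one of the preceding therapies, but preceding therapies not able to be administered in setting of resource limitation". Section 7.1 repeats that limb when it defines respiratory failure for the protocol as a whole: "Clinical diagnosis of respiratory failure (i.e., clinical need for one of the preceding therapies", followed by the same resource-limitation clause.

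**SAP.** Section 6.1.7 gives the derived variable. After the devices it ends with "or ECMO, or clinical diagnosis of respiratory failure", with no condition and no pointer to 1.c.i. The next bullet uses it directly: "Respiratory failure-free survival is defined as the combination of no respiratory failure (defined above) and no report of mortality from any cause". Section 8.1 says only "The primary efficacy endpoint is the proportion of participants alive and free of respiratory failure at Day 28", and Section 2.2.1.1 also leaves 1.c.i out. Section 8.2.3, for the secondary proportion with respiratory failure, uses the same short label but ties it to the criterion: "or clinical diagnosis of respiratory failure (exclusion criteria 1.c.i) at any time during the 28 days after randomization". Section 10 lists changes from the planned analysis, and this is not among them.

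**The concern.** In the protocol, the clinical-diagnosis limb is a narrow substitute. It covers a participant who needed one of the listed therapies at a site that could not supply it. Without the condition, the limb rests on a recorded label and no longer on need for a specific level of support.

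The distinction matters in this population. Entry requires severe illness, with signs such as SpO2 at or below 93% or PaO2/FiO2 below 300. The design also expects some participants to receive ordinary oxygen without counting as failures, since one secondary endpoint is defined as "Among patients that never experience respiratory failure in the first 28 days, time to initiation, duration, and proportion of subjects receiving supplemental oxygen". A recorded diagnosis without unmet need for a listed therapy is therefore conceivable.

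At stake is whether the reported primary result is the protocol's endpoint, and whether the primary and secondary respiratory-failure variables agree on the same participant.

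**Working it through.** The plan states no event rate, effect size or power, so there is no figure to reproduce. The check is a comparison of definitions, followed by the weight of one participant.

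**1. Classification of a participant alive at Day 28, each text read literally**

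| Profile | Protocol 1.c.i | SAP 6.1.7 (primary) | SAP 8.2.3 (via 1.c.i) |
|---|---|---|---|
| Intubated and ventilated | Failure | Failure | Failure |
| Recorded diagnosis; listed therapy needed but not available | Failure | Failure | Failure |
| Recorded diagnosis; no unmet need, no listed therapy | Not failure | **Failure** | Not failure |
| No recorded diagnosis, no listed therapy | Not failure | Not failure | Not failure |

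On this limb the texts part only in the third row.

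**2. Weight of one third-row participant**

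Inputs: Part 1 has 18 participants allocated 5:5:5:3 (5+5+5+3 = 18). Part 2 was planned at 72 randomized 1:1 (72/2 = 36 per arm). Both come from SAP 3.2. The shift in an arm's proportion is 100/n points:

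- Part 1 varespladib arm: 100/5 = 20.0 points
- Part 1 placebo arm: 100/3 = 33.3 points
- Planned Part 2 arm: 100/36 = 2.8 points

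The Part 1 figures assume tabulation by randomized arm at the allocated sizes. If the three active arms were pooled (n=15), the shift would be 100/15 = 6.7 points.

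**3. Direction in a two-arm comparison (illustration only)**

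Suppose the same share q of protocol non-failures in each arm is relabelled as failure. The failure rate f becomes f + q(1−f), so the risk difference is multiplied by (1−q). Assume placebo failure of 20%, 30% or 40%, varespladib at half of that, and q from 0 to 30%. The difference then shrinks from 10.0 to 7.0, from 15.0 to 10.5, or from 20.0 to 14.0 points. With 36 per arm and a two-sided 5% test, power falls from 22% to 9%, from 33% to 14%, or from 46% to 22%. None of these rates, nor q, is in the documents.

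**The case against.** The strongest reply is that 6.1.7 is shorthand. Clinical diagnosis of respiratory failure is the protocol's own label, and the protocol explains it each time it lists the definition. SAP 8.2.3 uses the same short form beside a citation of 1.c.i, and the SAP names the protocol as reference material. This makes shorthand a plausible intent. It does not settle the text: the citation in 8.2.3 governs a secondary endpoint, while 6.1.7 supplies the primary variable and carries no pointer.

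A reader might also infer more than the documents support:

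- **That AE terms or any charted diagnosis feed the primary endpoint.** No document says so. Where the SAP derives a variable from AE terms, as for organ failure in 6.1.7, it states this; for respiratory failure it names no such source. Protocol 10.3.1.1 bases the oxygenation and ventilation endpoints on the investigator's assessment of oxygen support, and Protocol 11.1.1 says that COVID-19 progression is not automatically an AE. The eCRF is not available.
- **That failure on low-flow oxygen is itself the error.** Under the protocol, too, such a participant fails if a listed therapy was needed but unavailable. Only the third row of the table diverges.
- **That the trial loses a known amount of power.** The rates, q and its equality across arms are assumptions. The sample size was not based on power, Part 2 had one subject at the pause, and Section 10 rules out tests and P values for Part 1 efficacy.
- **That the dropped condition causes a missing start date.** The time and duration formulas in 6.1.7 are based on devices, so a diagnosis-only failure has no device date under the protocol's narrow limb either. SAP 8.2.5 censors at Day 28 when neither death nor the event occurs, and Section 10 removes the subsetting for Part 1. This is a separate minor point.

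**Conclusion.** The inconsistency is real and specific. As written, the SAP's primary-endpoint rule is broader than the protocol's on the clinical-diagnosis limb. It differs from the SAP's own secondary definition in 8.2.3, and it is not declared as a change.

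Its practical size is unknown. It depends on whether any participant has a recorded diagnosis, no listed therapy and no unmet need for one, and on which data field supplies the diagnosis. The documents show neither. If one such participant exists, an arm's Part 1 proportion moves by 20 or 33 points. Any single reclassification in arms this small would do the same, but Section 10 now has summary statistics and confidence intervals reported for the Part 1 primary outcome.

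This should be fixed because the rule defines the primary endpoint and the correction is nearly free. The documents do not support treating it as a demonstrated bias or a demonstrated loss of power.

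**What to change.** In SAP 6.1.7, define respiratory failure by citing exclusion criterion 1.c.i in full, including the condition that a listed therapy was clinically needed but could not be administered because of resource limitation. State that other recorded diagnoses of respiratory failure do not count, and name the eCRF field that supplies this limb. Use the same definition in 8.1 and 8.2.3. Citing the criterion in full would also restore the delivered-oxygen fraction that 6.1.7 leaves out of the high-flow limb.

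If the broader definition is intended, declare and justify it in Section 10 as a change from the protocol.

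Separately, the SAP could say how a failure established only by unmet need is handled in the device-based time and duration formulas.

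The cost is SAP wording, plus at most a data query for any participant who qualifies by this limb alone. Sample size and planned tests are unaffected. For Part 1 the change belongs before database lock; for Part 2 it can go into the protocol and SAP amendment that Section 10 already announces for other endpoints.
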